8.7 Asthma Evaluation and Management (E&M) Visits

Every two months, an asthma E&M process will occur where participants' asthma medication regimen will be adjusted based on symptoms, albuterol/levalbuterol use, FEV₁, recent exacerbations, and their current level of therapy (see Section 7.1.1.2). At these visits, asthma and rhinitis endpoints, including the CASI (see Section 3) will also be measured. The E&M Visits will include:

- Pregnancy test (post-menarcheal females)
- Physical exam and AE assessment
- Vital signs, with height and weight

- Spirometry and peak flow
- CASI and other symptom measurements
- Assignment of asthma medication regimen by study clinician (see Section 7.1.1)
- Asthma education/counseling (see Section 7.1.1.5)

8.8 12-Month Visit

The 12-Month Visit is the final visit and will include:

- Pregnancy test (post-menarcheal females)
- Final physical exam and AE assessment
- Vital signs, with height and weight
- Blood draw
- Allergen skin test for German cockroach
- Spirometry and peak flow
- CASI and other symptom measurements
- Targeted pulmonary exam
- NAC
- Nasal lavage, before and after NAC

8.9 Early Termination Visit

Participants who withdraw from the study or are dropped from the study will be invited to the study center for an Early Termination Visit as specified in the Protocol ICAC-28 MOP. The Early Termination Visit can include:

- Pregnancy test (post-menarcheal females)
- Final physical exam and AE assessment
- Vital signs, with height and weight
- Blood draw
- Allergen skin test for German cockroach
- Spirometry and peak flow
- CASI and other symptom measurements

Procedures contraindicated by the medical condition of the participant will not be conducted at the discretion of the study clinician. For participants who refuse or are unable to come to the clinic, the final clinical assessment as described above may be conducted over the phone. Besides this visit, no further follow-up will be made, except for participants who are discontinued due to pregnancy or SAEs. These participants will be contacted to determine the outcome of the pregnancy or the SAE. Refer to Section 12.6, Pregnancy Reporting, for more information on AE reporting for pregnancy.

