11.2.2 Discontinuation of Study Participation

Participants may additionally be prematurely terminated from the study for the following reasons:

1. Pregnancy
2. The participant elects to withdraw consent from all future study activities, including follow-up.
3. The participant is "lost to follow-up" as defined in the Protocol ICAC-28 MOP.
4. The participant dies.
5. The Investigator no longer believes participation is in the best interest of the participant.
6. The participant has a need for > 3 bursts of systemic corticosteroids for asthma exacerbations during the treatment period OR has a need for > 2 bursts of systemic corticosteroids for asthma

exacerbations within 6 months during the treatment period. If prescribed by an ICAC study clinician, a burst is defined as a course for prednisone, prednisolone, or methylprednisolone will be 2 mg/kg/day as a single daily dose for 4 days with a maximum dose of 60 mg per day. The course for dexamethasone will be 0.3 to 0.6 mg/kg/day as a single daily dose for 2 days with a maximum dose of 16 mg per day. If a corticosteroid burst for the treatment of an asthma exacerbation is prescribed by a non-ICAC clinician, it will be counted regardless of dose.

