12.4 Collection and Recording of Adverse Events

12.4.1 Collection Period

Adverse events (including SAEs) will be collected from the time of consent until 30 days after a participant completes study participation or until 30 days after he/she prematurely withdraws (without withdrawing consent) or is withdrawn from the study.

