12.4.2 Collecting Adverse Events

Adverse events (including SAEs) may be discovered through any of these methods:

- Observing the participant
- Interviewing the participant
- Receiving an unsolicited complaint from the subject
- In addition, an abnormal value or result from a clinical or laboratory evaluation can also indicate an adverse event, as defined in Section 12.3, Grading and Attribution of Adverse Events

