12.4.3 Recording Adverse Events

Throughout the study, the investigator will record adverse events and serious adverse events as described previously (Section 12.2, Definitions) on the appropriate AE/SAE eCRF regardless of the relationship to study therapy regimen or study procedure.

Once recorded, an AE/SAE will be followed until it resolves with or without sequelae, or until 30 days after the end of study participation, or until 30 days after the subject prematurely withdraws (without withdrawing consent)/or is withdrawn from the study, whichever occurs first. The DAIT NIAID Medical Officer may request continued follow-up of an adverse event beyond the stated timeframe if deemed clinically important.

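### Protocol 8.9 ends follow-up at the Early Termination Visit except after a pregnancy or SAE exit, while 12.4 requires AE collection and follow-up to day 30 after withdrawal

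*Protocol*

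**What the plan says.** Protocol 8.9 covers children who withdraw or are dropped from the study. They are invited to an Early Termination Visit, which can include a final examination and AE assessment and may be done by phone if the child cannot or will not attend. The section then closes contact: "Besides this visit, no further follow-up will be made, except for participants who are discontinued due to pregnancy or SAEs". For the excepted children it adds: "These participants will be contacted to determine the outcome of the pregnancy or the SAE".

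Protocol 12.4 sets a different end point. Under 12.4.1, AEs and SAEs are collected from consent "until 30 days after he/she prematurely withdraws (without withdrawing consent) or is withdrawn from the study". Under 12.4.3, an event once recorded is followed until it resolves, or until 30 days after study participation ends, "or until 30 days after the subject prematurely withdraws (without withdrawing consent)/or is withdrawn from the study, whichever occurs first". This applies whatever the event's relationship to treatment. 12.4.3 also allows longer follow-up case by case: "The DAIT NIAID Medical Officer may request continued follow-up of an adverse event beyond the stated timeframe if deemed clinically important".

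The SAP has no rule on AE follow-up after a child leaves the study.

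**The concern.** Both sections apply to the same children and give different instructions about the same period. 8.9 decides who is contacted by the reason for leaving. 12.4 decides by whether an event is open and whether 30 days have passed. A site that follows 8.9 closes the record at the visit; a site that follows 12.4 keeps contact to day 30. Under 15.1.1 any departure from study procedures is a deviation, so for an affected child a site departs from one section whichever it follows.

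At stake is the completeness of safety follow-up in a pediatric allergen-injection trial that has safety as a secondary objective. Some exits follow worsening asthma or a judgement that staying is not in the child's interest, and the outcome of an open event is worth knowing in those children.

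**Working it through.** No statistical calculation applies; the check compares the texts.

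**1. Does follow-up in 8.9 mean only visits?** If it did, phone contact under 12.4 would be compatible with it. The exception shows otherwise. What it preserves for pregnancy and SAE exits is contact to learn an outcome, so the word covers safety contact as well as clinic visits.

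**2. How far does the exception reach?** It depends on why the child was discontinued, and it covers the outcome of that pregnancy or SAE. It does not reach:
- a non-serious AE open at the visit in a child who left for any other reason;
- an SAE open at the visit that was not the reason for leaving.

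**3. Who can fall outside it?**
- Protocol 11.2.2 item 5: "The Investigator no longer believes participation is in the best interest of the participant".
- Protocol 11.2.2 item 6, which includes: "The participant has a need for > 3 bursts of systemic corticosteroids for asthma exacerbations during the treatment period". Such a child is often not an SAE exit, because 12.2.4 does not class an asthma hospitalization as an SAE unless it is a suspected adverse reaction.
- A child who withdraws without withdrawing consent, a group that 12.4.1 and 12.4.3 name.
- Children under other withdrawal reasons tabulated in SAP 6.1, such as non-compliance, or an adverse event that is not serious.

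**4. Who is not affected?**
- Children who stop only the injections. Protocol 6.7 and 11.4 keep them in follow-up.
- Children who withdraw consent, because 12.4 exempts them.
- Children who die or are lost to follow-up, because contact is not possible.

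**5. When do the two rules collide?** Let *d* be the number of days from withdrawal to the Early Termination Visit. The period that 12.4 requires and 8.9 closes is 30 − *d* days when *d* is below 30, and nothing when *d* is 30 or more. At most it is 30 − 0 = 30 days. It ends sooner for an open event that resolves first. 8.9 refers to the MOP for the visit, and the MOP is not among the documents, so *d* is unknown.

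**6. What is lost if a site follows 8.9?**
- *Events open at the visit.* They are already recorded and will be reported; what may be missing is the outcome.
- *New events up to day 30.* 12.4.2 lists, as one way in which AEs come to light, "Receiving an unsolicited complaint from the subject". Unprompted reports can therefore still arrive, and the loss is in active collection.

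**7. Which analyses are touched?** The primary analysis uses nasal challenge scores and no AE follow-up data. Secondary endpoint 1 is limited by Protocol 3.3 to events in the course of treatment, and SAP 8.3.1 tabulates events and participants rather than outcomes, so it is little affected. The effect falls on general AE data.

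**The case against.** The strongest reply is that a site has good reason to follow Section 12. Protocol 12.1 presents that section as the place that defines the safety data and the procedures for collecting and recording them, and 8.1.2 refers the reader there for AE assessment. This stands in part: a reader might infer that the protocol gives no guidance at all, and that is too strong. Neither passage, however, says that Section 12 overrides 8.9. 8.9 deals with contact after exit on its own terms and cross-refers to 12.6 for pregnancy but not to 12.4.

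Two other provisions soften the conflict without removing it. The Medical Officer's power in 12.4.3 is discretionary and concerns time beyond the stated limit, so it does not restore the 30 days. The visit or call within 1 to 2 weeks in 8.10 is for children at Control Level 4 and concerns asthma symptoms, not AEs in general.

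A reader might also infer that adverse events drop out of the IND Annual Report, which covers all AEs (12.5.2.1). For events open at the visit this does not follow, because they are already on record.

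Finally, a reader might try to size the group from the six exit reasons in 11.2.2. The documents do not support that. They give no early-termination rate and no split by reason, SAP 6.1 lists further reasons, and a child who leaves for an affected reason need not have an event open at the visit.

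**Conclusion.** The inconsistency is real and should be corrected, but it is narrow. It arises when three conditions hold together: the child has left the study without withdrawing consent and can be reached; the Early Termination Visit falls before day 30; and safety follow-up that 12.4 still requires lies outside the pregnancy/SAE exception. The last condition covers a non-serious AE open at the visit, an open SAE that did not cause the exit, and active collection of new events.

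The consequence is missing outcomes and missed active collection for at most 30 days per child. How many children this concerns cannot be estimated from the documents. The conflict of wording is certain; its practical effect depends on visit timing in the MOP. The documents do not support reading this as a threat to the efficacy conclusion or as a material weakness in secondary endpoint 1.

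**What to change.** Make two edits in Protocol 8.9.

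1. In the sentence that ends follow-up, insert a further exception ahead of the existing one: *AE/SAE collection and follow-up to 30 days as required by Section 12.4 (by telephone where needed, for participants who have not withdrawn consent), and for*. The existing words on pregnancy and SAE exits then follow unchanged.
2. Open the next sentence with *Participants discontinued due to pregnancy or SAEs* in place of its first two words, so that contact to learn the outcome of the pregnancy or SAE stays tied to that group.

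The cost is one wording change, which needs IRB approval before use (Protocol 16.2) and can go with the next amendment, plus an occasional phone call. No analysis or sample size changes.

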8.10 Unscheduled Visits

Participants who experience asthma-related problems (not requiring emergency room care) or concerns between scheduled study visits will be seen by a study clinician as warranted by the situation. If the site staff are notified by the participant, his/her family, an ED, a hospital, or clinic that the participant was seen for an unscheduled visit elsewhere, the site staff will contact the participant within 2 weeks of discharge to obtain an update on the participant's clinical status. A follow-up visit at the study center

will be scheduled if needed. For details on the management plan, please refer to Section 7.1.1 and the Protocol ICAC-28 MOP.

Participants who are at Control Level 4 at a study visit will either be seen in the clinic or will receive a follow-up phone call within 1-2 weeks of the visit to check the status of their symptoms.

Participants who have 2 exacerbations within a 1-month period must be seen in a face-to-face visit to determine if continuation in the study is in the best interest of the participant.

8.11 Visit Windows

During dose escalation, 1-2 injections will be given each week separated by at least 2 days. Dose escalation must be completed over a maximum of 40 weeks (See Appendix B: Study Restrictions Due to COVID-19). Bi-weekly and monthly maintenance injections should be scheduled as close as possible to the every 2-week or every 4-week target dates.

See the Protocol ICAC-28 MOP for details regarding visit scheduling and Appendix A for the Table of Events.

9 Mechanistic Assays

Exploratory objectives will be addressed using mechanistic assays to evaluate biological responses to CR immunotherapy. Detailed descriptions of the methodology for biological sample collection and processing and for assay implementation are described in the ICAC-28 MOP and in separate mechanistic study proposals.

Whole blood will be collected by venipuncture according to the visit activity schedule (see Appendix A) prior to Randomization and at the 12-Month Visit or the Early Termination Visit. Nasal lavage samples will be collected prior to each NAC and at approximately 3 hours after the initiation of each NAC.

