3.1 Description of Study Design

This study is a randomized, double-blind, placebo-controlled, multicenter trial of non-standardized glycerinated German cockroach (*Blattella germanica*) allergenic extract or placebo treatment administered by subcutaneous injection.

Participants will be randomized to 1 of 2 treatment groups in a ratio of 1:1:

1. German cockroach allergenic extract administered by subcutaneous injection.
2. Placebo administered by subcutaneous injection.

Protocol ICAC-28 will enroll eighty 8 to 17-year-old cockroach sensitive children with asthma with a positive cockroach Nasal Allergen Challenge (NAC) before randomization.

The intended maintenance dose of German cockroach allergenic extract is ≈ 6 mcg of Bla g 2. The study will be based on a treatment schedule with German cockroach allergenic extract or placebo for 12 months.

There will be a Screening phase to determine eligibility, including a positive IgE and skin test to German cockroach. If asthma control parameters are not met, participants will begin a run-in period, during which participants' asthma medications will be adjusted for up to 4 months to achieve symptom control before completing an initial NAC procedure. Eligible participants with a positive NAC will then be randomized to one of the two treatment arms and receive their first injection. Up to 2 doses of SCIT will be given weekly during dose escalation, separated by a minimum of 2 days. Dose escalation can be delayed at any point for systemic or local reactions, although to continue to maintenance each participant will need to reach the minimum maintenance dose in a maximum of 40 weeks (see Appendix B: Study Restrictions Due to COVID-19). Once the maintenance dose is achieved, participants will receive two additional maintenance level-doses (for a total of three maintenance level-doses) spaced approximately 2 weeks apart, followed by maintenance injections every 4 weeks for the remainder of the treatment period.

At Randomization and every 2 months during treatment, an asthma Evaluation and Management (E&M) process will occur where participants' asthma medication regimen will be adjusted based on symptoms, albuterol/levalbuterol use, FEV₁, recent exacerbations, and their current level of therapy.

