8.6 Follow-up

8.6.1 SCIT Dose Escalation

The dose escalation of glycerinated German cockroach allergenic extract or placebo is detailed in the Dose Escalation Table 8.6.1. Each injection will be administered by the trained research staff under the

supervision of the study clinician along with any rescue medications, as required. Refer to the ICAC-28 Reaction Orders on handling treatment-related reactions.

During the dose escalation phase, all females who have reached menarche will be required to have a urine pregnancy test monthly.

Prior to the administration of each dose of allergenic extract or placebo, pre-assessment will be completed to assess the eligibility of the participant to receive the allergenic extract injection.

Post-assessment of participants, 30 minutes after each injection, will be completed for symptoms or changes.

During all dosing visits, a study clinician and appropriate emergency supplies will be readily available to treat any adverse reactions.

Participants will receive weekly injections during escalation (Table 8.6.1). From Dose 1 through Dose 20, injections must be separated by a minimum of 2 days. From Dose 21 through Dose 26, injections must be separated by a minimum of 5 days. To maximize flexibility during dose escalation, injections can be given once weekly, and can be delayed at any point if there are systemic reactions, local reactions or other concerns. To continue on to maintenance, each subject will need to reach the minimum maintenance dose in a maximum of 40 weeks (see Appendix B: Study Restrictions Due to COVID-19).

Dose escalation will be conducted by the following schedule(s):

Table 8.6.1 SCIT Dose Escalation

All participants will start SCIT with Dose 1. Doses -1 and -2 are included for participants who experience a reaction at Doses 1 or 2 that require dosage reductions.

Dose #	Concentration	Volume
-2	1:10,000	0.03 ml
-1	1:10,000	0.04 ml
1	1:10,000	0.05 ml
2	1:10,000	0.1 ml
3	1:10,000	0.2 ml
4	1:10,000	0.3 ml
5	1:10,000	0.4 ml
6	1:1,000	0.05 ml
7	1:1,000	0.1 ml
8	1:1,000	0.2 ml
9	1:1,000	0.3 ml
10	1:1,000	0.4 ml
11	1:100	0.05 ml
12	1:100	0.1 ml
13	1:100	0.2 ml
14	1:100	0.3 ml
15	1:100	0.4 ml
16	1:10	0.05 ml
17	1:10	0.1 ml

18	1:10	0.2 ml
19	1:10	0.3 ml
20	1:10	0.4 ml
21	1:1	0.05 ml
22	1:1	0.1 ml
23	1:1	0.15 ml
24	1:1	0.2 ml
25	1:1	0.3 ml
26	1:1	0.4 ml

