Dose escalation will continue according to the schedule unless there are lapses in dosing or reactions occur. Dosing modifications as a result of reaction or lapse in dosing during dose escalation are detailed in the MOP for Protocol ICAC-28.

Participants who are unable to reach the minimum maintenance dose (the highest volume of the 1:10 concentration; Dose 20 in Table 8.6.1) by 40 weeks following the start of dose escalation will be unable to proceed to the maintenance period and will have their study therapy stopped (see Section 11.2.1; see Appendix B Study Restrictions Due to COVID-19).

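### Protocol 3.1 and 8.11 allow injections 2 days apart throughout dose escalation, but 8.6.1 requires at least 5 days between Doses 21 to 26, the strongest ones

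*Protocol*

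**What the plan says.** Three protocol sections set the spacing of escalation injections.

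- **Section 3.1:** "Up to 2 doses of SCIT will be given weekly during dose escalation, separated by a minimum of 2 days".
- **Section 8.11:** "During dose escalation, 1-2 injections will be given each week separated by at least 2 days".
- **Section 8.6.1:** "From Dose 1 through Dose 20, injections must be separated by a minimum of 2 days", and then "From Dose 21 through Dose 26, injections must be separated by a minimum of 5 days".

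Sections 3.1 and 8.11 make no exception by dose and do not send the reader to 8.6.1 for spacing. Section 8.11 refers to the manual of procedures and Appendix A for scheduling. In Table 8.6.1, Doses 21 to 26 are the six rows labelled 1:1. Appendix A, footnote 5, gives 16 to 26 weeks as the normal length of escalation, with up to 40 if needed.

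The 40-week limit is also worded in two ways. Section 8.11 has "Dose escalation must be completed over a maximum of 40 weeks". Section 8.6.1 has "each subject will need to reach the minimum maintenance dose in a maximum of 40 weeks", and defines that dose as Dose 20. Sections 3.1, 6.7 and 11.2.1 also refer to the minimum maintenance dose.

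**The concern.** Someone who schedules visits from the visit-window section or the design overview would find nothing against giving two of the top-strength injections 2 or 3 days apart. Someone who works from the dosing section would find that forbidden. Section 15.1.1 makes any departure from study procedures a protocol deviation, so the same visit could be coded as compliant or as a deviation depending on the section read.

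The conflict falls on the strongest injections, given to children with asthma. Section 5.2 lists rush schedules among the risk factors for fatal reactions and says that this trial does not use one, so the protocol itself treats the pace of dosing as a safety matter.

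**Working it through.** **Inputs.** Table 8.6.1 has 26 doses from Dose 1 on (Doses -1 and -2 serve only for reductions after reactions). Doses 1 to 20 come before the 1:1 rows, and Doses 21 to 26 are those rows. The maximum rate is two a week (3.1, 8.11). The minimum gap is 2 days throughout (3.1, 8.11), or 2 days and then 5 days from Dose 21 (8.6.1).

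**1. Reproduce Appendix A.** Take two a week for Doses 1 to 20 and one a week for the last six: 20/2 + 6/1 = 16 weeks. Take one a week throughout: 20 + 6 = 26 weeks. Both ends of the 16 to 26 weeks are recovered. The 16 assumes that a 5-day minimum becomes a weekly visit in practice.

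**2. Shortest escalation under each rule.**

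| Rule | Arithmetic | Weeks |
|---|---|---|
| 3.1 and 8.11, two a week throughout | 26/2 | 13 |
| 8.6.1, strict 5-day gaps for the last six | 10 + 6 × 5/7 | about 14.3 |
| 8.6.1, last six given weekly | 10 + 6 | 16 |

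The interval rules alone account for 14.3 − 13 = 1.3 weeks. The other 16 − 14.3 = 1.7 weeks come from rounding 5 days up to a weekly visit.

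**3. Dose 21 to Dose 26 (five intervals).**

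- 5-day minimum: 5 × 5 = 25 days.
- Bare 2-day minimum, ignoring the weekly maximum: 5 × 2 = 10 days.
- Two a week, evenly spaced: 5 × 3.5 = 17.5 days, or 2.5 weeks.

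**4. One gap tested against all three sections.** Suppose Doses 22 and 23 are 3 days apart. Since 3 ≥ 2, this meets 3.1 and 8.11. Since 3 < 5, it breaks 8.6.1. Two a week, evenly spaced, means a 3.5-day gap, so that rate cannot be kept up in the 1:1 rows without breaking 8.6.1.

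**5. The 40-week wording, side by side.** Section 8.11 speaks of completing escalation and names no dose and no consequence. Section 8.6.2 uses completed escalation as the condition for starting maintenance injections. The provisions that stop therapy are 6.7, 8.6.1 ("unable to reach the minimum maintenance dose (the highest volume of the 1:10 concentration; Dose 20 in Table 8.6.1) by 40 weeks") and 11.2.1. All three use the minimum maintenance dose. The per-protocol samples in Protocol 13.4.1 and SAP section 5 require escalation to 0.4 mL of the 1:10 dose, which is the same threshold, and neither mentions week 40 or Dose 26.

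**The case against.** The best defence is that this is general text against specific text. A gap of 5 to 7 days satisfies all three sections at once, because two a week is a maximum and 2 days is a minimum. Section 8.6.1 is the detailed dosing section, and Appendix A's 16 weeks follows from its rule and not from the 13-week reading. The manual of procedures, which was not available for this review, may settle scheduling in practice.

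Much of this stands. A careful site could have met every section, and the documents do not show that any site used short gaps at the top strength. But 3.1 and 8.11 still permit what 8.6.1 forbids, and the protocol does not say which section governs. The manual could guide sites, but it would not remove the contradiction from the protocol.

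A reader might also infer that the 40-week wording decides who has therapy stopped, and so who enters the per-protocol sample. That would require 8.11 to mean Dose 26, so that a participant at Doses 20 to 25 at week 40 fails it. The documents do not support this. Section 8.11 names no dose and contains no stopping provision, and 8.6.2 lets completion be read as readiness for maintenance. The stopping provisions and the per-protocol definitions agree on the Dose 20 threshold. Section 8.11 is at most ambiguous.

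**Conclusion.** The interval conflict is real. For Doses 21 to 26, two sections allow gaps that a third forbids. The size is 25 days against 10 days on the bare minimum (17.5 days at an even two a week) from Dose 21 to Dose 26. Over the whole escalation the shortest course is about 13 weeks against about 14.3. The tempting contrast of 13 with 16 weeks overstates the effect of the rules, since 16 assumes weekly visits for the last six doses.

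These figures assume no reactions, lapses or delays. The documents give no reaction rate by interval, so the effect on safety cannot be put in numbers. The match with Appendix A shows which spacing is consistent with the stated duration; it does not establish which interval is clinically right, and no view on that is offered. The 40-week difference is a secondary matter of wording.

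**What to change.** - Reconcile Protocol 3.1, 8.11 and 8.6.1 so that one interval rule per dose range appears in every place, and check that Appendix A's duration follows from it. The clinical team decides the rule.
- Align 8.11's 40-week sentence with the minimum-maintenance-dose wording in 3.1, 6.7, 8.6.1 and 11.2.1, or explain the difference. Sections 6.7 and 11.2.1 already agree with 8.6.1 and need no change.
- SAP 7.2 and 8.1.2 describe randomization and injection scheduling in the past tense. If dosing is over, state which interval rule was applied, list the gaps between Doses 21 and 26 from the dosing records, and check that deviations were coded against that one rule.

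The cost is a wording change and a memo to sites or, after dosing, one listing and a check of deviation codes. Sample size and the primary analysis are unaffected.
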